A randomized control design will be used to test the efficacy of the CHW intervention to improve HTN control among South Asian individuals with diabetes in Atlanta. The intervention will recruit participants from three clinical sites in Atlanta, GA: 1) The Emory Family Medicine Clinic is located in North Atlanta and serves approximately 1,200 unique South Asian patients annually; 2) Grady Clinic at Brookhaven is a safety net county clinic that sees a high volume of low-income South Asians (approximately 6,000 per year; 3). The Shifa Free Clinic is a community-based free clinic coordinated by the Islamic Circle of North America, Atlanta branch, to serve uninsured and under-insured South Asians in Georgia.. On average, they see 200 unique South Asian patients per month at each site. Both Emory Family Medicine Clinic and Grady Clinic utilize EHR systems which will be used to generate lists of eligible patients for the intervention. Shifa Clinic is currently transitioning to an EHR system, thus patient data will be electronically accessible for patient recruitment and follow-up outcome data. Each of the sites has expressed interest and commitment to participating in the study. The community centers will not be engaged in research, all consenting and procedures will be completed by Emory study staff.

We also anticipate enrolling participants from community-based recruitment with the CHWs referring participants that they meet at South Asian community events and advertising the study. The proposed research design is a modified stepped wedge design, whereby 2 groups will implement the intervention in phases. The time prior to the intervention will serve as the comparison group. Enrolled patients will be randomized to treatment (Group A) and wait-list control (Group B) groups within each site.

There are five primary research groups for this study: 1) 326 treatment participants who will receive the CHW intervention; 2) 326 control participants who may receive the CHW intervention as a point of service at a later point; 3) 10 subjects who will participate in provider surveys; 4) 25 subjects who will participate in qualitative key informant interviews; 5) a retrospective EHR review of characteristics of South Asians seen at Emory Healthcare and NYU hospital system between 2014 and 2019; and 6) 50 subjects who will participate in focus groups.

B2. CHW Component:

1. Data collection and consenting with treatment participants

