After letters from the provider practices of the 3 participating clinical sites have been mailed to eligible patients or they have been notified of the study by their provider, CHWs will contact patients via mailing and phone calls to invite them to enroll into the intervention. CHWs will call patients a maximum of ten times over a two-week period at varying times of day to invite them to enroll into the study. In addition, list of eligible treatment participants will be shared with primary care physicians who will be encouraged to refer patients to contact CHWs during routine visits. CHWs will also table at primary care provider (PCP) clinics and community events to enhance recruitment and enrollment. During the recruitment call, CHWs will conduct a brief screening to confirm eligibility (see Screening Form). If eligible, patients will be invited to complete an in-person consent form (See Consent Brochure and Consent Signature Page for CHW Intervention) and survey (see Participant Survey) that assesses baseline demographic and logistical information, such as preferred language and session availability. Participants must sign a consent form in order to participate, which will be administered by the CHW or bilingual study coordinator.

Surveys will be collected from all participants at baseline and 6 months. Baseline surveys will be conducted by a CHW or bilingual study coordinator immediately following consent. Six-month surveys will be conducted in person by a study staff within two weeks of completion of the CHW coaching component of the intervention. Survey measures will be developed based on their 1) brevity; 2) presence of domains with face validity for Asian American or low literacy communities; and 3) valid psychometric properties, thus enhancing scientific rigor. Survey measures include weight and blood pressure measurements, as well as questions about self-efficacy, medication adherence, and referrals to social services.

Patient-engagement measures: Contact with eligible treatment group participants will be collected in REDCap or on paper-based CRFs, including phone contact attempts, patients' intervention status (declined, enrolled, not reached etc.), completion of intervention activities (such as health education sessions and phone-based health coaching), and completion of data collection, referrals, and intervention activities across sites and CHWs.

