Practices that express interest in participating in the CHW intervention will sign a Memorandum of Understanding (MOU) that outlines the nature of the evaluation and the uses of any data collected, including:

Intervention Components

A minimum set of proposed intervention components will be implemented including:

- 5 group-based health education sessions on hypertension and diabetes management
- Provision of culturally and linguistically tailored health information and resources

- Two one-on-one in-person meetings that can be at the participants home or at the participants clinical site and 7 follow-up phone calls to engage in goal-setting activities regarding changes to health behaviors, medication adherence, or other issues related to diabetes prevention as identified jointly by patient and CHW.
- Participants will develop with the CHW and receive a copy of their long-term and short-term Participant Action Plan.
- Referrals to other services available in the community (i.e. exercise classes, social services, mental health, tobacco cessation, etc.

CHW Curriculum

Participants enrolled in the CHW intervention will receive group-based health education sessions:

Curriculum Session Title & Content	Tailored cultural components

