During the study period, the research team will be performing a retrospective chart review of South Asians, using surnames to identify patients of South Asian origin. We will submit a waiver of consent to obtain these records.

VII. DATA COLLECTION AND ANALYSES

A. PHASE 2: Data collection and implementation of the CHW intervention (recruitment, consenting, CHW led education sessions) will be led by Emory University. All participants will attend Session 1. Everyone who attends will receive a unique study identifier that will associate a specific study number with the participant. This information will then be downloaded onto the NYU servers into R statistical software for randomization. We will use stratified randomization by age and gender to assign patients to intervention or control arms.. The table necessary to link patient identifiers and the study ID will be maintained by the Emory-based study coordinator to ensure that patient confidentiality is maintained.

Treatment Participants

The study ID will be used for all implementation activities and reporting on CRFs. Thus, patients who are observed more than once will have the same study ID in each extract, which is necessary for the planned analyses. Study data will be collected in the form of a survey at baseline and at endpoint. Follow up calls and visits will also be recorded in REDCap, or paper-based CRFs and kept in locked boxes until transport back to the Emory Dunwoody offices for input into REDCap and secure storage.

A random sample (n=50) of less engaged and more engaged previously enrolled treatment group participants of the CHW intervention will receive an invitation to participate in the focus group. This will be a one-time anonymous audio-recording with no follow-up; no names or identifying information will be collected at the time of the focus group.

The focus group will be completed in-person or virtually via Zoom (Emory University has HIPAA compliant Zoom accounts which have been institutionally approved for telemedicine, see supporting documentation) to accommodate the current COVID-19 situation. The method (face-to-face vs. virtual) will be determined at the discretion and preference of the participants, while following institutional regulations for COVID-19. Recordings will only include audio (not video).

Control Participants

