The control participants will all participate in baseline and endpoint surveys with the CHWs. They will also complete a Session 1 educational session. Control participants will not be contacted during the rest of

the 6-month intervention phase and will be contacted by the clinic staff only when the intervention is complete among treatment participants. Those in the first wave will be offered the intervention in the second wave. The second wave control group will be offered educational sessions as a point of service and not as part of research (i.e., wait-listed control study design).

B1. Data Analysis and Monitoring

The NYU site will lead the data analysis portion of the study, with input and feedback from Emory research staff.

Specific Aim 2 Analysis.

Specific Aim 2: To compare the effect of the intervention with usual care on achieving BP control among individuals with diabetes. The primary outcome will be the proportion of eligible patients at a practice site to achieve BP control (130/80 mmHg) six months following the index office visit. *Hypothesis:*

Individuals receiving care during the implementation of the intervention will be more likely achieve BP control six months following the index office visit than individuals receiving care as usual. The primary outcome of interest is the proportion of patients who achieve BP control. The secondary outcomes of interest include changes in HbA1c, SBP and DBP, and BMI at 6 months. For analyses of both primary and secondary outcomes, a logistic regression model will be used to estimate the CHW effect on outcomes (see equation 1):

$$(1) \quad \text{logodds}[P(Y_{ij})] = \beta_0 + \gamma_j + \beta_1 H$$

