Using the primary outcome, HTN control, as an example, Y_{ijk} indicates state of HTN control at the end of the 6 months for patient i , in clinic site j . $Y_{ijk}=1$ if patient achieved HTN control, $Y_{ijk}=0$ if otherwise. $H_i=1$ if patient i was randomized to the CHW intervention, $H_i=0$ if otherwise (i.e., control group). γ_j is a fixed effect for clinic site. $\mu + b_j$ is the log odds of HTN control for patients randomized to the control group in the first 6 months. β_1 represents the log odds ratio of HTN control for those randomized to the CHW intervention compared to those randomized to the control group. A test will be conducted with the following null and alternative hypotheses: $H_0 : \beta_1 = 0$ vs. $H_A : \beta_1 \neq 0$ to assess whether or not the CHW intervention had an effect on HTN control after 6 months. We will conduct exploratory, secondary subgroup analyses to see which subgroups may achieve greater benefit from the intervention. In addition, we will assess an alternative measure of HTN control, using an ADA BP control definition of 140/90 mmHg to evaluate the effect of the CHW intervention. And finally, we will compare the findings from this Atlanta-based study with our ongoing trials in the NYC area. The datasets from each respective study will not be combined; they will be analyzed separately. Sex as a biological variable will be addressed by exploring gender as a potential moderator of intervention effects.

Specific Aim 3: Analysis

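### Equation (1) leaves out baseline BP and the age and gender strata, and no planned analysis allows for CHW in the treatment arm: a loss of precision and possibly too narrow an interval, not an invalid test

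*Combined protocol and SAP*

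**What the plan says.** - **Randomisation.** Section VII.A (Phase 2): "We will use stratified randomization by age and gender to assign patients to intervention or control arms". Section III.B1: "Enrolled patients will be randomized to treatment (Group A) and wait-list control (Group B) groups within each site".
- **Primary analysis.** Section VII.B1: "The primary outcome of interest is the proportion of patients who achieve BP control". Equation (1) is a logistic model with an intercept, the arm indicator and a site term that "is a fixed effect for clinic site". Gender otherwise appears only as an exploratory moderator.
- **Baseline BP.** Section III.B2: "Surveys will be collected from all participants at baseline and 6 months", and "Survey measures include weight and blood pressure measurements".
- **Delivery.** Section IV.A1 lists "5 group-based health education sessions on hypertension and diabetes management", two one-on-one meetings and seven calls. Under Control Participants in VII.A, controls receive only Session 1 and the two surveys. Section VII.B3 gives a caseload of about 16 per full-time CHW per six months.
- **CHW records.** Section III.B2 tracks "completion of data collection, referrals, and intervention activities across sites and CHWs". No analysis in the visible text, main or sensitivity, has a CHW term, a cluster-robust standard error, an ICC or a design effect.

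**The concern.** There are two gaps of different kinds.

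The first is efficiency and coherence. Three factors shape randomisation (site, age, gender), but only site reaches the model. The outcome is a BP threshold, so baseline BP is the obvious prognostic variable. Section VII.B2 says that everyone is uncontrolled at baseline, so the information lies in the continuous reading, which is collected but not used.

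The second is the validity of the interval. If some CHWs coach better than others, patients of the same CHW have correlated outcomes in one arm only. A site effect does not absorb that variation, and equation (1) would report too narrow an interval.

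**Working it through.** **1. The plan's own figure.** Inputs from VII.B2: 15% vs 35%, two-sided 0.05, 80% power, 10% loss.

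n per arm = [1.96·√(2·0.25·0.75) + 0.8416·√(0.15·0.85 + 0.35·0.65)]² / 0.20² = 72.4, so 73. Then 73 × 1.1 = 80.3, so 81 per arm, or 162 in total, as stated. With 81 × 0.9 = 72.9 followed, power is 80.3%. At the planned 326 per arm, 326 × 0.9 = 293 are followed and power is 99.99%.

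**2. Covariates.** The documents give no BP correlation, so it is assumed. Simulation: 2,000 replicates, 293 per arm, three sites, 3 age × 2 gender strata balanced between arms (latent correlation with outcome 0.2), two correlated BP covariates.

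| Added to equation (1) | Risk-difference SE ratio | Half-width (points) | Log-odds-ratio SE | Log odds ratio |
|---|---|---|---|---|
| none | 1 | 6.8 | 0.206 | about 1.12–1.13 |
| strata only | 1.000 | 6.8 | – | – |
| strata + BP, r = 0.3 | 0.980 | 6.7 | 0.217 | 1.22 |
| strata + BP, r = 0.5 | 0.937 | 6.4 | 0.232 | 1.38 |
| strata + BP, r = 0.6 | 0.910 | 6.2 | 0.247 | 1.51 |

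On the log-odds scale the SE rises, but the estimate moves further from zero. Mean z is up 3%, 8% and 11% (strata alone, 1%).

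If those correlations apply before selection on uncontrolled BP (75% in VII.B3), range restriction gives a variance ratio u² = 0.535. With r' = r·u/√(1 − r² + r²u²), r' = 0.22, 0.39 and 0.48, and the SE ratios become 0.997, 0.961 and 0.942. Hence about 0 to 9%.

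In a separate simulation with assumed covariate effects, equation (1) had type I error of 3.6 to 4.8%. Omitting the strata does not inflate it.

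**3. CHW clustering.** The documents give neither an ICC nor a number of CHWs. Assumed: ICC 0.01 to 0.05. Caseload 16 gives 326/16, about 20 CHWs. If each CHW serves two waves, 32 each gives about 10.

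- Design effect in the treated arm: DE = 1 + (m − 1)·ICC.
- SE = √[(0.1275 + 0.2275·DE)/293]. With DE = 1 it is 3.48 points: half-width 6.8, lower limit 13.2.
- Coverage of equation (1)'s interval = 2Φ(1.96/SE ratio) − 1.
- Corrected interval: Satterthwaite df, with (CHWs − 1) for the treated arm and 292 for controls.
- Difference needed for significance: smallest d with d = t·√[(0.1275 + (0.15 + d)(0.85 − d)·DE)/293].

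Example, m = 16 and ICC 0.05: DE = 1 + 15 × 0.05 = 1.75; SE = √[(0.1275 + 0.3981)/293] = 4.24 points; ratio 1.217; df 32.9; t = 2.035; half-width 8.6.

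| CHWs (m), ICC | DE | SE ratio | Coverage of eq. (1) | Corrected interval wider by | Lower limit | Difference needed |
|---|---|---|---|---|---|---|
| 20 (16), 0.01 | 1.15 | 1.047 | 93.9% | 8% | 12.6 | 6.7 |
| 20 (16), 0.05 | 1.75 | 1.217 | 89.3% | 26% | 11.4 | 7.8 |
| 10 (32), 0.01 | 1.31 | 1.095 | 92.7% | 17% | 12.0 | 7.2 |
| 10 (32), 0.05 | 2.55 | 1.412 | 83.5% | 55% | 9.4 | 9.7 |

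Without CHW, the difference needed is 6.2 points. Using followed rather than enrolled patients per CHW (293/20 = 14.7) changes little: DE is 1.68 instead of 1.75 at ICC 0.05.

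A simulation (2,500 replicates, null 15% in both arms, ICC 0.01 and 0.05) gave type I error for equation (1) of 4.8% and 7.9% with 20 CHWs, and 6.7% and 12.8% with 10. The adjusted model with CHW-clustered errors gave 4.4% and 4.8%, and 5.6% and 5.0%.

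**4. Where the reassurance ends.** Allowing for CHW, power at 15% vs 35% stays at 96% or more in all four rows.

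- At 162 enrolled, 81/16 is about 5 CHWs. With 73 followed per arm, t-based power is 68.5% to 54.2% for ICC 0.01 to 0.05.
- VII.B3's chain gives 462 × 0.40 = 185 enrolled and 462 × 0.5 × 0.4 × 0.9 = 83 followed per arm. Power is 85% ignoring CHW and, with 5 CHWs, 73.4% to 57.3%.
- At 652 enrolled with only 5 CHWs, power falls below 80% above an ICC of about 0.047.

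**The case against.** The strongest reply is that nothing here is broken. Equation (1) is a valid test under the stratified randomisation, the strata add almost nothing numerically, and the BP gain rests on assumed correlations. The CHW figures rest on an assumed ICC and number of CHWs. Under the null, inflation arises only if CHW effects average zero yet vary; if coaching does nothing at all, there is none. The plan also does not say that one CHW serves each participant throughout, and VI.A has each session held several times a month.

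All of this stands, and it limits the size of the point. It does not remove it. The trial will report an effect with an interval. If CHW effects vary around a real benefit, that interval is too narrow even when the p-value is tiny.

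A reader might also infer that first-wave controls who enter the second wave make the standard error wrong. The documents do not support that. VI.A and VII.A describe no re-randomisation of these people, and VII.B1 speaks of controls in the first 6 months. Counting them again as treated would raise a question of bias, not of standard errors.

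**Conclusion.** Both omissions are confirmed, and both are worth mending. Baseline BP is a modest, near-free gain in precision. The strata make the analysis match the randomisation. CHW clustering matters only if CHW effects vary; if they do not, equation (1)'s interval is not too narrow.

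Two stronger readings should be resisted. One is that leaving out the strata, or ignoring CHW, invalidates the trial: at 652 enrolled, 15% vs 35% and about 10 to 20 CHWs, the expected conclusion is the same either way, and it would change only for observed differences of roughly 6 to 10 points. The other is that the conclusion is therefore safe at any size: it is not shown to be so at 162 or about 185 enrolled, or with very few CHWs. The documents do not settle which enrolment will apply. The ICC, the number of CHWs and the BP correlations are assumptions throughout.

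**What to change.** 1. **Primary model.** logit P(Y = 1) = b0 + b1·arm + site + age stratum + gender + baseline SBP + baseline DBP. State the age cut-points. Give a site category to community-recruited participants (III.B1). Use the BP reading taken before randomisation, since III.B2 places the baseline survey immediately after consent and the Documentation of Consent section within two weeks of it. Report a standardised risk difference with 95% CI beside the odds ratio.
2. **One prespecified sensitivity analysis for CHW in the treatment arm.** Use cluster-robust standard errors with Satterthwaite df, or a partially nested random intercept, with controls as single-patient clusters. State that controls' contact with CHWs at Session 1 and at the surveys is ignored.
3. **State that each person is analysed only in their first randomised period.**

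**Cost.** No new outcome data. Age, gender and BP are already collected; activities are already tracked by CHW, so the identifier only has to be carried into the analysis file. The odds ratio becomes conditional on the covariates, which is why the risk difference is reported with it. The sensitivity interval is wider by the amounts in the table; even at ICC 0 the smaller df widen it by about 3% with 20 CHWs (t = 2.014) or 6% with 10 (t = 2.076). Fix these choices before outcomes are seen by arm.

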Type 2 Diabetes Mellitus	E11.00, E11.01, E11.21, E11.22, E11.29, E11.311, E11.319, E11.321, E11.329, E11.331, E11.339, E11.341, E11.349, E11.351, E11.359, E11.36, E11.39, E11.40-E11.44, E11.49, E11.51, E11.52, E11.59, E11.610, E11.618, E11.620-E11.622, E11.628, E11.630, E11.638, E11.641, E11.649, E11.65, E11.69, E11.8, E11.9, E13.00,	Therapeutic class of Antihyperglycemic, excluding medication names of Metformin and Acarbose	A1C: 4548-4, 7426-0, 4549-2, 17856-6, 59261-8, 71875-9, 62388-4, 4637-5, 55454-3, 41995-2, 17855-8

	E13.01, E13.10, E13.11, E13.21, E13.22, E13.29, E13.311, E13.319, E13.321, E13.329, E13.331, E13.339, E13.341, E13.349, E13.351, E13.359, E13.36, E13.39, E13.40-E13.44, E13.49, E13.51, E13.52, E13.59, E13.610, E13.618, E13.620, E13.621, E13.622, E13.628, E13.630, E13.638, E13.641, E13.649, E13.65, E13.69, E13.8, E13.9		
--	---	--	--

V. STUDY ENROLLMENT

A. Characteristics of the research population

The overall number of subjects expected to participate in this study is 737. This includes a total enrollment of 652 participants in the CHW Intervention (326 treatment participants and 326 control participants, accounting for 10% attrition), 10 subjects who participate in the provider surveys, 25 participants in the key informant interviews and 50 focus group participants.

CHW Intervention

Inclusion Criteria: Participants will be eligible for study participation if they meet the following criteria: a) are of South Asian ethnicity (identified through a race and language code in the EHR or at screening); b) are at least 21 years of age and younger than age 85, c); d) a diagnosis of diabetes in the EHR or self-reported through community recruitment and e) a diagnosis of hypertension or self-reported diagnosis through community recruitment; f) an uncontrolled BP reading(>130/80mmHg) in the last 6 months or at screening.

Exclusion Criteria: a) Patients under the age of 21 and older than 85 will be excluded. b) Women who are pregnant at the time of screening. c) Type 1 diabetes or diabetes secondary to other conditions (e.g. steroid-induced, pancreatic insufficiency, or chemotherapy-induced), d) inability to perform unsupervised physical activity.

No children will be enrolled in this study.

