B3. Sampling. Across the three clinical sites, there will be approximately 3,600 unique South Asian patients that have had an office visit in the last year. Based on preliminary analysis of [name] patient panel, we estimate 30% of those individuals will have a Type II Diabetes diagnosis (n=1080), and estimate that 60% will have co-morbid diabetes and HTN (n=648), 75% of these individuals will have uncontrolled HTN (n=486), and additional 5% will be excluded due to not meeting other eligibility criteria, leaving 462 individuals eligible for the study. Of these individuals, approximately 50% will be randomized to the treatment group, and we estimate based on our previous studies that 40% of patients will be interested in the study and consent to enroll into the study (n=326). Based on retention rates from our CHW studies,^{12,95,96,98,128,129,131} we estimate that approximately 90% of individuals in control and treatment quarters will be followed up at six months (n=83). Thus, across sites, we will enroll approximately 652 patients per six-month period, resulting in total recruitment of approximately 326 treatment group participants across 3 practice sites. Treatment group participants will be matched to 326 control group participants. Approximate CHW caseload over a six-month period is 16 participants for a full-time CHW.

Specific Aim 3 Analysis.

B4. Analysis to address this aim will be guided by the questions in **Table 4**.

Table 4: Guiding Questions

Utilization Patterns	
 • How frequently do clinicians utilize the intervention? • What is the percentage of adoption? • Does the utilization pattern change over time?
Physician Attitudes Regarding the Integrated Intervention	
 • What are physicians' attitudes regarding CHW approaches to diabetes and HTN management? • How satisfied are the physician's with the integrated intervention tools? • What are the barriers and facilitators of using the CHW integration components? • How does the intervention affect clinicians' satisfaction with workflow around T2DM management?

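### The allocation strata are described in three unreconciled ways, and community recruits are given no site level in a primary model built on clinic site

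*Combined protocol and SAP*

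**What the plan says.** **Allocation.** Three statements describe it.
- Section III.B1 (Overall Design for Phase 2): "Enrolled patients will be randomized to treatment (Group A) and wait-list control (Group B) groups within each site". Age and gender are not mentioned.
- Section VII.A (Phase 2), the operational description of randomisation in R: "We will use stratified randomization by age and gender to assign patients to intervention or control arms". Site is not mentioned, and there are no age cut-points.
- Section VII.B3 (Sampling): "Treatment group participants will be matched to 326 control group participants".

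**Who is recruited.** Section III.B1 starts with clinics: "The intervention will recruit participants from three clinical sites in Atlanta, GA". It then adds a second route: "We also anticipate enrolling participants from community-based recruitment with the CHWs referring participants that they meet at South Asian community events". Section III.B2 also has CHWs recruiting at community events. The inclusion criteria in V.A accept "a diagnosis of diabetes in the EHR or self-reported through community recruitment", with a parallel allowance for hypertension, so a community recruit needs no clinic record.

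**Primary analysis.** Section VII.B1 (Specific Aim 2 Analysis) first words the primary outcome as a proportion of eligible patients at a practice site. Later in the same section, and in II.B (Study Outcomes), it is a proportion of patients with no site condition. In equation (1) the response "indicates state of HTN control at the end of the 6 months for patient" i in clinic site j, and the γ term "is a fixed effect for clinic site". The model contains site and arm but neither age nor gender.

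**The concern.** There are two linked gaps.

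First, a programmer working from VII.A would build strata from age and gender, and one working from III.B1 would build them from site. The three clinics are a family medicine clinic, a county safety-net clinic and a free clinic for uninsured and under-insured patients, so balance by setting plausibly matters. The factors named in VII.A are also not the factor in the model.

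Second, the model needs a value of j for every patient, and nothing says what that value is for someone met at a community event. The analyst could leave such people out, attach them to a clinic, or create a new level. These choices can give different primary results, and nothing stops the choice from being made after outcomes are known. Leaving people out would remove randomised participants from the primary analysis.

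**Working it through.** **1. The plan's own sample size.** Inputs from VII.B2: 15% versus 35%, two-sided 0.05, 80% power, 10% loss. With pooled variance under the null and p̄ = 0.25:

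n per arm = [1.96·√(2·0.25·0.75) + 0.842·√(0.15·0.85 + 0.35·0.65)]² / 0.20² ≈ 72.4, so 73.

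Inflating by 73/0.9 gives 82 per arm (164 in total); 73 × 1.10 gives 81 per arm (162 in total). With 162 × 0.9 / 2 = 72.9 evaluable per arm, power is 0.803. The stated 162 and power above 80% are reproduced. Neither site nor any stratum enters this calculation, so the point here is specification, not arithmetic.

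**2. How many participants might lack a clinic site.** The documents give no community share. A rough guide is the gap between the target of 652 (III.B1) and what the clinics would yield under VII.B3's fractions: 30% with diabetes, 60% of those with hypertension, 75% of those uncontrolled, 95% otherwise eligible, 40% consenting.

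| Annual clinic pool | Eligible | Enrolled at 40% | Shortfall from 652 |
|---|---|---|---|
| 3,600 (VII.B3) | 462 | 185 | 467 (72%) |
| 7,200 (III.B1: 1,200 + 6,000, free clinic not counted) | 923 | 369 | 283 (43%) |
| 9,600 (adding 200 × 12 = 2,400 for the free clinic) | 1,231 | 492 | 160 (24%) |

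The last row assumes that monthly counts at the free clinic can be added over a year for one location. With VII.B3's 462 eligible and 100% consent, 652 − 462 = 190 (29%) would still come from elsewhere.

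**3. How far VII.B3 can be trusted.** It attaches n = 326 to 40% consent among the half randomised to treatment, but 462 × 0.5 × 0.40 = 92. Its 83 followed up equals 92.4 × 0.9. The chain therefore fits an enrolment near the 162 of VII.B2, not 652. The 72% subtracts a yield on the smaller scale from a target on the larger one, so it is an upper figure and not a planned community share.

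**4. Cost if participants without a site were dropped.**
- From 652 to 185, the standard error of the log odds ratio grows by about √(652/185) = 1.88.
- Power with 185 × 0.9 / 2 = 83.25 per arm: Φ[(0.20·√83.25 − 1.96·0.612) / 0.596] = Φ(1.05) ≈ 0.85.
- If accrual were only 162, power would be 0.76, 0.68 or 0.51 with 10%, 25% or 50% community recruits dropped. These shares are assumptions. At that size the 185 expected from the clinics would suffice without community recruits.

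**5. Leaving stratification factors out of the model.** In a simulation with assumed stratum control rates of 5%, 10%, 20% and 25%, a two-sided 0.05 test that ignored the balanced strata had type I error of 0.043 (N = 146) and 0.046 (N = 586). The test is slightly conservative, not invalid.

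**The case against.** It can fairly be said that the allocation sentences are compatible: stratify by age and gender inside each site. That stands as a possible reading. A reader might infer that randomisation ignores site, but VII.A does not say that age and gender are the only factors. The passages are unreconciled, not strictly contradictory.

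A reader might also infer a biased comparison. The documents do not support that: allocation is random under either reading, and the site term adjusts for chance imbalance between clinics.

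Nor do the documents say that community recruits are excluded or belong to no clinic. Some may be patients of a participating clinic, participants come to the Emory Dunwoody Clinic to consent (VI.A), and two of the three outcome statements carry no site condition. All of this stands, but none of it is a rule assigning a level of j.

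Finally, the 72% and the 1.88-fold standard error are tempting headline figures. They rest on VII.B3's inconsistent inputs, on one year's patient list although the plan has two waves, and on treating the whole shortfall as people without a site. They should be read only as the upper end of a range. The documents also give no BP control rates by site or recruitment route, so how prognostic these factors are is unknown.

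**Conclusion.** The concern holds as a specification gap. The plan gives no single set of strata, and, applied literally, the primary model cannot place community recruits. The consequences are possible loss of randomised participants from the primary analysis and room for a choice made after the data are seen.

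The size is uncertain. The implied shortfall is about 24% to 43% on III.B1's volumes and at most 72% on VII.B3's. All three assume 652 enrolled, 40% consent and VII.B3's eligibility fractions, and they overstate the affected share to the extent that community recruits are clinic patients. Precision is not the main worry at the larger target, since power would be about 0.85 with 185 left, given 15% versus 35% and 10% loss. The point should be settled before outcomes are examined by arm, but it does not invalidate the trial.

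**What to change.** 1. Record recruitment source (Emory, Grady, Shifa, community) at screening, before randomisation, with a stated rule for someone reached by both routes.
2. In III.B1 and VII.A, state one set of strata: recruitment source, gender and broad age group, with the age cut-points. If randomisation has started, keep the existing list and make only the changes below.
3. In VII.B1, define j as recruitment source with community as its own level, and add the age and gender stratification factors to equation (1).
4. In VII.B1, define the primary outcome over all randomised participants.
5. In VII.B3, delete the statement that controls are matched.

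The cost is one more factor in the randomisation script, one field on the screening form and a few sentences of protocol text. The downside is more strata: two age groups give 4 × 2 × 2 = 16 cells, about 41 participants each at 652 but about 10 each at 162. Age should therefore be kept to a few broad groups.
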